2.2 Trial Design

Phase 1

- Validity testing: content validity index (CVI), cognitive interviews, construct validity testing
- Feasibility trial
- Reliability testing (inter-rater reliability)

Phase 2

[figure not shown]
- Randomised controlled trial (cluster group randomization by GP practice, intervention arm (ADRe Profile implementation), control arm (standard of care))

Phase 3

- Interviews and survey with participants of phase 2

2.3 Study Scheme Diagram

[figure not shown]
Figure 1: study scheme diagram

SU Non CTIMP Healthcare Research Protocol

Figure 2: RCT flow diagram

3. Subject Selection

3.1 Number of Subjects and Subject Selection

Content Validity Index sample size n = 10

Participants: a convenience sample of 2 GPs, 2 pharmacists, 2 nurses working in general practice/community and 2 care assistants working in general practice/community and 2 patients

Recruitment strategy: advertise in research networks and the university

Contrast group sample size n = 2x20

Participants: a convenience sample of up to 20 service users > 64 who do not take prescribed medicines daily.

Recruitment strategy: Advertise in research networks and the university

Cognitive interview sample size n = 5

Participants: a convenience sample of 1 patient, 1 nurse working in general practice/community, 1 care assistant working in general practice/community, 1 GP + 1 pharmacist

Recruitment strategy: Advertise in research networks and the university

Inter-Rater Reliability sample size n = 20 + 30 = 50

Participants: 20 service users from 2 general practices, >64, with >4 prescribed medicines.

Recruitment strategy: Approach cluster areas in Swansea Bay UHB and Hywel Dda UHB. Invitation by letter and/or email. General practice to identify suitable patients and approach them to invite for participation.

Randomised Controlled Trial sample n = 60

Participants: 6 new general practices x 10 patients and practice / district nurses or nurse assistants

SU Non CTIMP Healthcare Research Protocol

Recruitment strategy: approach all 8 GP clusters in Swansea Bay UHB and 7 clusters in Hywel Dda UHB by post and/or email. General practice to identify suitable patients and approach them to invite for participation.

Calculation of the sample size:

RCT (sample = 60): Previously, in a 'before and after' single arm intervention study, with participants acting as their own controls, 17/19 (89%) had improvement in at least 1 clinical problem when ADRe Profiles for polypharmacy were used (Jordan et al submitted). We hypothesised that 9/19 (47%) would have shown some improvement without intervention, necessitating an effective sample of 40 patients (20 in each arm), with 5% significance and 90% power (Uitenbroek 1997). Based on the reported intra-cluster coefficient (0.02), (Jordan et al 2015), and a design effect of 1.18, to achieve an effective sample size of 40, we need an actual sample size of 48 (Killip et al 2004). 10 patients in each of 6 clusters (GP practices) allows for 20% loss to follow up, which is realistic in general practice, where either patient or nurse may be unavailable for follow up.

Survey sample size: up to 3 nurses, 3 pharmacists, 3 GP's and up to 30 service users.

For the survey, all health professionals involved with the intervention arm (n=9) and all service users in the intervention arm (n=30) will be included. The aim is to gain stakeholder views on the intervention.

Qualitative semi-structured interviews sample size - 3 nurses, 3 pharmacists, 3 GP's and 3 service users

For the qualitative interviews, a convenience sample of 12 participants will be selected. This will include all nurses, GP's and pharmacists in the intervention arm, as well as a purposive sample of 3 patients. The patients will be selected based on the most positive and most negative responses in the survey. The aim is to gain stakeholder views on the intervention and to supplement and illustrate the RCT data.

Phase 1

- **Content validity index respondents:** healthcare professionals (current or retired, working full-time or part-time, willing to participate and sign informed consent), service users (age > 64, willing to participate)
- **Cognitive interview respondents:** healthcare professionals (current or retired, working full-time or part-time, willing to participate), service users (age > 64, willing to participate and sign informed consent)
- **Contrast group validity respondents:** group A (people, age >64, no daily prescribed medicines - vitamin and nutritional supplements and moisturising skin preparations will not be counted as 'medicines', willing to participate and sign informed consent), group B (as below)
- **Inter-rater reliability and feasibility participants:** service users (age > 64 years, with a long-term condition, prescribed > 5 medications daily. (Vitamin and nutritional supplements and moisturising skin preparations will not be counted as 'medicines'.), Willing and able to give informed, signed consent themselves, or where capacity is lacking in the opinion of their nurses, a consultee/representative accompanying the patient who is willing to give advice and assent to the service user participating and sign on their behalf.

Phase 2

Service users:

- age > 64 years
- with a long-term condition
- prescribed > 5 medications daily. (Vitamin and nutritional supplements and moisturising skin preparations will not be counted as 'medicines'.)
- Willing and able to give informed, signed consent themselves, or where capacity is lacking in the opinion of their nurses, a consultee/representative accompanying the patient who is willing to give advice and assent to the service user participating and sign on their behalf.

Nurses:

- Working in or alongside a general practice and expected to work there for the next 6 months, willing to participate and sign informed consent

Pharmacists and GP's:

- Aligned with the general practice, expected to stay in employment for the next 6 months, willing to participate and sign informed consent

Phase 3

No new participants, we shall approach people who took part in Phase 2.

3.3 Exclusion Criteria

Phase 1

- **Content validity index respondents:** not willing to participate
- **Cognitive interview respondents:** not willing to participate
- **Contrast group validity respondents:** not willing to participate
- **Inter-rater reliability and feasibility testing respondents:** age < 64 years, without any long-term conditions, prescribed < 5 medications daily, not willing to participate, unable to consent and no consultee/representative present, not fluent in English or Welsh (unless a family member can assist with translation), receiving palliative care, expected to remain in the practice for the next 12 months

Phase 2

Service users:

- Age < 64 years
- Without any long-term conditions
- Prescribed < 5 medications daily
- Not willing to participate
- Unable to consent and no consultee/representative present
- Not fluent in English or Welsh (unless a family member can assist with translation)
- Receiving palliative care

- Expected to remain in the practice for the next 12 months

Nurses:

- Unwilling to participate, unwilling to administer ADRe Profile

Pharmacists and GP's:

- Unwilling to participate, unwilling to review ADRe Profile

Phase 3

No new participants.

Recruitment and identification of personal Consultees: In the event that a participant lacks decision-making capacity regarding participation in the study a personal consultee will be identified to provide advice. The Consultee may be their next of kin, family member, a friend, an unpaid carer, other relative in regular contact. The Personal Consultee will have an unpaid or non-professional role in caring for the person.

The consultee will be identified by the practice nurse as they will likely accompany the service user to the GP practice or respond to the invitation to participate on behalf of the service user. The consultee will be contacted to provide a information about the study (Participant Information Sheet for consultees) and they will be asked for their advice regarding the inclusion of the person and what the person's views would have been regarding inclusion in the research if they had capacity to make the decision for themselves. If they are happy to be a Personal Consultee, they will sign the consent form for consultees.

In the event that a Personal Consultee cannot be identified, or is not willing or able to act (for example due to their own illness or infirmity), the service user will not be included in the study.

The Consultees will have as much time as they need to consider the study and will have the opportunity to ask the practice nurse/or the researcher questions before giving their advice regarding the inclusion of the person lacking capacity.

The practice nurse/researcher will obtain written confirmation that the Consultee has provided consent by means of a Consultee dated signature on the Consultee Declaration Form, and dated signature of the person who presented and obtained the declaration.

The original signed form will be retained in the participant's medical records, a copy will be provided to the researcher for the ADRe Study site file in the ADRe office, and copies will be offered to the participant or his/her family and the consultee.

Parts of the study involve single contact with researcher, so there is little scope for non-compliance (content validity index, cognitive interviews, construct validity, survey, interviews). The feasibility trial (n=20) and the intervention arm of the trial (n=30) involve 3 and 5 points of contact (in person or virtual), respectively. If the participant becomes too unwell to respond to ADRe, and there is no consultee available, they will not be asked to complete a 2nd ADRe. However, unless informed otherwise, we shall retain collected data and collect information from patients' notes as originally planned.

4. Study Procedures

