4.5 Schedule of Assessment (in Diagrammatic Format)

Phase of study	Intervention arm	Control arm
Phase 1 - feasibility	Medical notes accessed for items to populate ADRe Profile	No control
	Self-completed ADRe Profile	
	Researcher-completed ADRe Profile	
Phase 2 – RCT step 1	Medical notes accessed for items to populate ADRe Profile	Medical notes accessed for items to populate ADRe Profile
	Self-completed ADRe Profile	Standard of care
	Nurse or researcher-completed ADRe Profile	Standard of care
Phase 2 – RCT step 2	Medical notes accessed for items to populate ADRe Profile	Medical notes accessed for items to populate ADRe Profile
	Self-completed ADRe Profile	Standard of care
	Researcher-completed ADRe Profile	Standard of care
Phase 3 – Survey and interviews	Survey administered to service user participants	
	Interviews performed with selected	

	participants (3 service users, 3 nurses, 3 GP's, 3 pharmacists)	
--	---	--

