4.12 Subject Withdrawal

Criteria for participant withdrawal:

- participant's /consultee's wishes
- physical deterioration, where continuing with the research would represent a burden on the participant
- failure to engage in participation
- move into long-term care facilities
- prolonged hospitalisation

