4.13 Data Collection and Follow up for Withdrawn Subjects

Unless requested otherwise, data that has been already collected will be kept for withdrawn participants.

5. Laboratories (if applicable)

N/A

6. Safety Reporting

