7.1 Primary Endpoint Efficacy Analysis

Differences between before and after the intervention will be calculated for: problems addressed, prescription regimens, NHS use, and compared, adjusting for site. The impact of age, diagnoses, and medicines' use (numbers and types of medicines prescribed) will be accounted.

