Data will be entered into excel via the electronic version of ADRe, imported into SPSS and described for the before and after ADRe administrations. Statistical analysis: differences between before and after the intervention will be calculated for: number and nature of problems addressed, prescription regimens, and NHS use. The impact of GP practice, age, diagnoses, and medicines' use (numbers and types of medicines prescribed) will be described and accounted for in exploratory bivariate and multivariate regression analyses. To explore the recorded changes and potential for further clinical gains, putative aetiologies of service users' signs and symptoms will be ascribed, using clinical information from medical and nursing records, including, but not restricted to, information on ADRe, and the list of medications prescribed (and over the counter). The ascription will be checked by supervisors using manufacturers' literature and formularies. Juxtaposition of ADRe and medication lists will generate suggestions for changes to improve the processes and possibly the outcomes of care. The prevalence of problems on the before and after profiles will be compared with two by two contingency tables, using McNemar's test for related dichotomous variables (Altman 1991).

Survey

Data will be described using the Statistical Package for Social Sciences (SPSS) and later combined with the interview results.

Interviews and recorded ADRe consultations

All interviews (and relevant parts of ADRe consultations) will be transcribed verbatim by the researcher/professional transcriber and anonymised. Transcripts will be

SU Non CTIMP Healthcare Research Protocol

coded, categorised, analysed and interpreted alongside the data of all completed cases, to identify, analyse and report patterns within data (Braun and Clark, 2006). The transcripts will be analysed by the team using the constant comparative method which will provide a systematic, re-iterative way of comparing and contrasting emerging codes, categories and concepts and ensure that theoretical perspectives are embedded in the description of change. Two researchers ([name]) will ensure validity of the analysis and verify interpretation. Disagreements will be resolved through discussion at team meetings. Diaries/logs will also be analysed in association with interview transcripts.

Triangulation

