8.3 Case Report Form

Swansea Trials Unit's forms will be adapted for use in CRF (with permission)

1 List of ADReGP Case Report Forms

Number	Title
FORM 01	Inclusion Criteria
FORM 02	Exclusion Criteria
FORM 03	Eligibility review
FORM 04	Randomisation/Enrolment
FORM 05	Patient Details (age and gender)
FORM 06	Baseline Medical Conditions
FORM 07	Baseline Medication list
FORM 08	Baseline ADRe Profile from available medical notes
FORM 09	Baseline Self-completed ADRe Profile
FORM 10	Baseline Nurse/researcher-completed ADRe Profile
FORM 11	Endpoint Medical Conditions
FORM 12	Endpoint Medication list
FORM 13	Endpoint ADRe Profile from available medical notes
FORM 14	Endpoint Self-completed ADRe Profile
FORM 15	Endpoint Nurse/researcher-completed ADRe Profile
FORM 16	Adverse Events
FORM 17	Serious Adverse Events
FORM 18	End of Treatment
FORM 19	Details of Death
FORM 20	Consent Withdrawal
FORM 21	PI Declaration
QUESTIONNAIRES	Patient survey Nurse survey GP survey Pharmacist survey

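### Section 3.3 prints an expected 12-month stay in the practice as a reason to exclude patients, the reverse of what the trial's second data collection needs; separately, patients on exactly 5 medicines fall between two rules

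*Combined protocol and SAP*

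**What the plan says.** **Length of stay.** Section 3.3 is the exclusion list. For Phase 1 reliability and feasibility respondents it ends with "receiving palliative care, expected to remain in the practice for the next 12 months". For Phase 2 service users the last item is again "expected to remain in the practice for the next 12 months". The inclusion criteria that precede section 3.3 handle staff the other way round: nurses, pharmacists and GPs qualify only if they are expected to stay for 6 months.

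**What the RCT collects and analyses.** Section 4.5 has two RCT steps. At step 2, as at step 1, both arms have the entry "Medical notes accessed for items to populate ADRe Profile". Section 8.3 lists baseline forms and endpoint Forms 11 to 15, among them "Endpoint ADRe Profile from available medical notes". Section 7.1 states: "Differences between before and after the intervention will be calculated for: problems addressed, prescription regimens, NHS use, and compared, adjusting for site". Section 7.5 repeats the approach: "differences between before and after the intervention will be calculated for: number and nature of problems addressed, prescription regimens, and NHS use".

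**Medicine count.** The synopsis and the section 3 inclusion criteria require more than 5 daily medicines, for Phase 1 reliability and feasibility participants and for Phase 2 service users. The title and section 1.2 describe people on 5 or more. The synopsis (contrast group), section 3.1 (inter-rater reliability) and section 7.5 (contrast group) describe the 20 Phase 1 participants as being on more than 4. Section 3.3 excludes those on fewer than 5.

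**The concern.** An exclusion criterion tells the person screening whom to turn away. As printed, the tenure line turns away the patients who can be expected to be there for a second look at their notes, and admits those who are not. The RCT analysis is built on change between two records, so the rule points in the wrong direction for the design it serves.

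The rule is operative text. Under section 4.2 a member of the patient's usual care team does the screening, and section 8.3 provides forms for inclusion, exclusion and eligibility review. A practice that follows the line recruits patients expected to leave. A practice that enrols the patients evidently intended departs from the written protocol. The text should not leave that choice to the screener.

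The medicine count raises a smaller question of the same kind: whether the people the title describes are the people the inclusion rule lets in.

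**Working it through.** No figure in the plan depends on this point, so the check sets the texts side by side.

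**Length of stay**

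1. *Direction of the printed rule.* An item in section 3.3 is a reason not to enrol. Expected to stay 12 months means excluded; not expected to stay means not excluded by this item.
2. *Neighbouring items.* Every other Phase 2 service-user item is a recognisable reason not to enrol: too young, no long-term condition, too few medicines, unwilling, unable to consent without a consultee, not fluent in English or Welsh without family help, in palliative care. Only the tenure item reads as a desirable property.
3. *Staff criteria.* An expected stay of 6 months is a condition of entry for staff. The patient item has the opposite sign.
4. *Step 2 data (section 4.5).* The intervention arm has notes access plus self-completed and researcher-completed Profiles. The control arm has notes access and standard care. Notes access is therefore the only step 2 data source for controls.
5. *Analysis (sections 7.1 and 7.5).* A before-after difference needs a second record for each patient. Rules 1 and 5 pull in opposite directions.
6. *Phase 1.* Section 4.5 shows one round of notes access, self-completion and researcher completion. No second time point is at risk, so the line there is a wording error without a design consequence.
7. *Correction elsewhere.* None in the visible text. Figures 1 and 2 and the contents of the forms are not shown, so it is unknown whether they repeat the line.

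**Medicine count, in whole numbers**

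| Rule | Where | Admits |
|---|---|---|
| more than 5 | synopsis and section 3 inclusion criteria | 6 or more |
| 5 or more | title, section 1.2 | 5 or more |
| more than 4 | synopsis and section 7.5 (contrast group), section 3.1 (inter-rater reliability) | 5 or more |
| excluded if fewer than 5 | section 3.3 | leaves 5 or more |

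The rules differ at one value, exactly 5. Such a patient is in the stated population and is not excluded, but fails inclusion. The more-than-4 and more-than-5 descriptions concern the same 20 people: the contrast-group entry in the inclusion criteria refers on to the reliability and feasibility participants, and section 7.5 identifies the medicated contrast group as the participants in ADRe testing. The exclusion of fewer than 5 does not by itself contradict a rule of more than 5; it only leaves a gap at 5.

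**The case against.** The strongest reply is that this is a plain slip. The intent is clear from the rest of the list, screeners will probably supply the missing word, and a rule that barred every settled patient would be likely to surface at the first screening. That stands, and it is why the point is an internal inconsistency and not a criticism of a design decision. It does not make the printed criterion right.

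A reader might go further and infer more than the documents support:

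- *That the trial would lose more than its allowance.* Section 7.4 allows 20% loss, 60 − 48 = 12 patients. No interval between step 1 and step 2 is given (section 4.6 is marked as not applicable), and someone who leaves within 12 months but after step 2 supplies both records. The number lost cannot be derived.
- *That the arms would differ.* Under section 4.3 patients consent before randomisation and the same rule applies to all, so no bias between arms follows.
- *That leavers lose their endpoint data through the withdrawal rules.* Section 4.12 lists "move into long-term care facilities" as a reason for withdrawal, and section 4.13 says that, unless requested otherwise, "data that has been already collected will be kept for withdrawn participants". No text says that such a move means leaving the practice, so this link is not relied on. The text before section 4 also keeps notes collection for participants too unwell for a second Profile with no consultee available; that does not cover leavers, but it shows that incomplete follow-up was considered.
- *That enrolling settled patients would bring sanctions.* Section 8.8 describes a general non-compliance log and says nothing about this criterion.

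The medicine count is a separate issue and adds nothing to the weight of the tenure line.

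**Conclusion.** The tenure line in section 3.3 is wrong as written in both places. In Phase 2 it conflicts with the step 2 notes access, the endpoint forms and the before-after analysis; in Phase 1 it is a wording error only. It is evidently a dropped word in an operative criterion. It should be corrected, but it does not rank among defects that threaten the trial's conclusions. No number of affected patients, bias or power loss can be stated. The reading assumes that the undisplayed figures do not reverse the rule.

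The medicine-count conflict is confirmed and minor. It touches one value, exactly 5, and the documents do not give the share of patients at that value.

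**What to change.** 1. In section 3.3, put the word not at the start of the tenure criterion, for Phase 1 reliability and feasibility respondents and for Phase 2 service users. Alternatively, move the criterion as it stands to the inclusion lists.
2. Reconcile the medicine count to one threshold consistent with the stated population, across the title, synopsis, section 1.2, section 3.1, the section 3 inclusion criteria, section 3.3 and section 7.5.
3. Check that Forms 01 to 03 carry the corrected wording.

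The cost is a wording amendment, notified as section 8.6.1 already provides, and a check of three forms. Sample size, data collection and analysis are unchanged.

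### If McNemar's test is run on completed ADRe Profiles, intervention patients too unwell for a second Profile leave the pairs and the before/after result leans towards improvement; section 7.5 has no rule for them

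*Combined protocol and SAP*

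**What the plan says.** The compliance paragraph at the end of section 3 (after 3.3) covers a participant who deteriorates between the two Profiles: where such a person "becomes too unwell to respond to ADRe, and there is no consultee available, they will not be asked to complete a 2nd ADRe". It goes on to say that, unless the team is told otherwise, "we shall retain collected data and collect information from patients' notes as originally planned".

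Section 4.12 lists reasons for withdrawal. Some are health-related: "physical deterioration, where continuing with the research would represent a burden on the participant", prolonged hospitalisation, and a move into long-term care. Others are not, such as "failure to engage in participation". Section 4.13 keeps data already collected from withdrawn participants and says nothing about a missing second Profile.

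Section 4.5 and the form list in 8.3 show three kinds of Profile at each time in the intervention arm: notes-based (Forms 08 and 13), self-completed (09 and 14) and nurse/researcher-completed (10 and 15). The control arm has only the notes-based kind.

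Section 7.5 states: "The prevalence of problems on the before and after profiles will be compared with two by two contingency tables, using McNemar's test". It does not say which kind of Profile enters the test, how an incomplete pair is treated, or what happens if a different person answers the second time. No sensitivity analysis is described.

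**The concern.** McNemar's test compares patients who lost a problem with patients who gained it, and it needs both observations. The skip rule in section 3 is triggered by getting worse, so the pairs most likely to vanish are those in which a problem appeared. Removing them shrinks the count of new problems and leaves the count of resolved problems largely intact. McNemar's test is the only hypothesis test named for the RCT in 7.5, where the regressions are called exploratory. A favourable before/after result could therefore partly reflect who was well enough to be asked twice.

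A second, weaker strand concerns the respondent. The skip applies only when no consultee is available, which implies that an available consultee may answer or help. The first Profile could then be the patient's own report and the second partly someone else's.

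**Working it through.** **The plan's own figures.** Section 7.4 gives an effective sample of 40, then 48, then 60. The design effect is 1 + (10 − 1) × 0.02 = 1.18; 40 × 1.18 = 47.2, given as 48; 48 / 0.80 = 60. The 40 itself reproduces with a one-sided pooled test (38 to 40) and comes close with a two-sided unpooled variance (42); a two-sided pooled test gives 48. None of this is at issue here. What carries forward is an intervention arm of 30, of whom 30 × 0.80 = 24 have both Profiles under the planned 20% loss.

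**Assumptions.** The documents give no rate of worsening, no rate of skipped second Profiles and no discordant counts. Everything below is illustrative.

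**Effect on one McNemar table.** With b problems resolved and c new, the exact two-sided p is 2 × P(X ≤ min(b, c)) for X ~ Binomial(b + c, 0.5). The table removes k of the c worsened pairs:

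| Resolved v new, all pairs | k = 0 | k = 1 | k = 2 | k = 3 | k = 4 |
|---|---|---|---|---|---|
| 10 v 4 | 0.18 | 0.092 | 0.039 | 0.012 | 0.002 |
| 9 v 5 | 0.42 | 0.27 | 0.15 | 0.065 | 0.021 |
| 8 v 6 | 0.79 | 0.58 | 0.39 | 0.23 | 0.11 |

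For example, 10 v 4 gives 2 × 1471 / 16384 = 0.18, and 10 v 2 gives 2 × 79 / 4096 = 0.039. The shift is always in the same direction, but whether it crosses 0.05 depends on the starting counts.

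**False positives under no net change.** In 20,000 simulated arms of 30 with 20% improving, 20% worsening and 60% unchanged, a significant improvement was declared as follows:

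| Share of worsened patients with no second Profile | Mean number lost | False significant improvement |
|---|---|---|
| 0% | 0 | 1.2% |
| 25% | 1.5 | 3.6% |
| 50% | 3.0 | 9.2% |
| 75% | 4.5 | 23.6% |
| 100% | 6.0 | 57.0% |

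The last row assumes that every worsened patient is lost and nobody else is. It is an extreme, not a forecast.

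**Effect on the proportion with at least one problem improved.** Suppose 21 of 24 completers (87.5%) improve, close to the 89% in 7.4. If k of the 6 lost had not improved and the rest improved at the completers' rate, the rate in all 30 is (21 + (6 − k) × 0.875) / 30:

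- k = 2: 24.5 / 30 = 81.7%
- k = 4: 22.75 / 30 = 75.8%
- k = 6: 21 / 30 = 70.0%

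**What a sensitivity analysis must do.** Take the 10 v 2 table with two worsened pairs missing, both free of the problem at baseline. Counting those two only as not improved leaves 10 v 2 and p = 0.039, because McNemar's test ignores concordant pairs. Counting them as having the problem at endpoint restores 10 v 4 and p = 0.18.

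**The case against.** The strongest reply is that 7.5 does not say the test uses completed Profiles. Section 3 continues notes collection for patients who are too unwell, and notes-based Profiles exist at both times in both arms. A comparison of Form 08 with Form 13 would keep these patients. This stands: the bias is conditional on the Profile source. It does not dispose of the point, because the plan has not chosen the source and 7.5 can equally be read as meaning the completed Profiles.

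A reader might infer that deteriorating patients are the only ones with a missing second Profile or a consultee's input. The documents do not support that. Section 4.12 includes non-engagement, 7.4 attributes loss to the unavailability of patient or nurse, and the Phase 2 inclusion criteria admit people lacking capacity through a consultee from the start. What is true is narrower: the stated skip rule is tied to deterioration.

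A reader might also infer that a change to a consultee overstates improvement because the consultee misses symptoms. No passage says that a consultee answers the symptom items; their described role is to advise on inclusion and sign. A relative in regular contact might report more problems than the patient, not fewer. The nurse-completed Profile also draws on observation and vital signs. No direction can be assigned.

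Finally, 8.3 lists form titles, not contents. It cannot be said that the respondent goes unrecorded, only that no such field is described.

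**Conclusion.** The point holds in conditional form. If McNemar's test is applied to completed Profiles, patients who become too unwell leave the pairs in the intervention arm only, and the before/after comparison is biased towards improvement. The direction rests on one assumption: that those lost for health reasons gained problems more often than they lost them. The amount cannot be estimated from the documents. The illustrations show that two or three missing worsened patients among 30 could matter, but the underlying counts are assumed. A change of respondent is a possibility implied by the wording, with a bias of unknown direction. This is a modest weakness that is cheap to close. It is not evidence that the trial's result will be wrong.

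**What to change.** 1. In 7.5, name the Profile source for McNemar's test and use the same source at both times.
2. Add a notes-to-notes comparison, Form 08 v Form 13. It keeps patients skipped under section 3. Section 4.13 should also say whether notes collection continues after a health-related withdrawal, since it now mentions only data already collected.
3. Add a sensitivity analysis for patients with no second Profile for health reasons. Count them as not improved in the proportion with at least one problem improved, and as having the problem at endpoint in the McNemar tables.
4. Record the respondent (patient / consultee / both) on Forms 09, 10, 14 and 15, if the forms do not already do so. Repeat the analysis without respondent-changed pairs as a sensitivity analysis only, because making that restriction the main analysis would itself remove deteriorated patients.

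Form 13 should not be set against a completed baseline Profile. Section 1.3 reports a mean of 2 problems detected without the Profile and 9 with it in one study, so unrecorded problems would look resolved.

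The cost is a little more analysis, one tick box per form, and a possibly less favourable before/after result.
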